The proposed double-blind laboratory study in 35 non-treatment seeking dependent smokers will determine the test the effect of greenwashing on behavioral economic self-administration and smoking topography. A within-subjects design will compare self-administration choice and smoking topography between two “brands” that in reality will be identical cigarettes with ads/labels that include vs. lack greenwashed tactics. Behavioral economic sessions will determine self-administration under concurrent availability of the two brands at various behavioral prices. Topography sessions will test ad-lib self-administration for each brand. Together, these sessions encompass the two primary ways advertising could affect smoking behavior (the amount smoked, and how one smokes). We hypothesize that greenwashed cigarettes will (a) show greater self-administration than non-greenwashed cigarettes when available at equivalent prices, (b) show reduced sensitivity to price compared to non-greenwashed cigarettes, and (c) will be self-administered more than non-greenwashed cigarettes even when their price is higher. We also hypothesize that in topography sessions greenwashed cigarettes will show: greater (a) total puff volume, (b) mean puff volume, (c) mean

Date: February 18, 2023

Principal Investigator: [name].

Application Number: IRB00264306

NCT04595279

puff duration, (d) mean maximum flow rate, (e) number of puffs; and lesser (f) mean inter-puff interval.

3. Background (briefly describe pre-clinical and clinical data, current experience with procedures, drug or device, and any other relevant information to justify the research)

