A difference in any behavioral economic demand metric would be meaningful for the cigarette market, and traditional reinforcement measures do not examine all reinforcement aspects. For example, greater demand intensity for greenwashed compared to non-greenwashed cigarettes would indicate that greenwashing would increase cigarette consumption at the lower end of price ranges. Greater demand elasticity for greenwashed cigarettes compared to non-greenwashed cigarettes would indicate that greenwashing would increase cigarette consumption at higher prices in the commercial market, even if greenwashing had little or no effect at lower prices. Using progressive ratio breakpoint (a traditional reinforcement measure that corresponds to demand elasticity) would allow the study to miss meaningful differences in demand intensity. Using discrete choice (a traditional measure which typically uses a low price for both alternatives and is therefore analogous to demand intensity) would allow the study to miss difference in demand elasticity. Moreover, by examining reinforcer interactions (cross-price elasticity), demand analyses can inform the degree to which smokers would pay more for greenwashed cigarettes even if non-greenwashed cigarettes were available at a lower price. Therefore, the primary aims of the proposed study are to test the effect of greenwashing on behavioral economic self-administration measures. Additional topography measures will be conducted to determine smoking topography during ad-lib self-administration. Together, these sessions encompass the two primary ways advertising could affect smoking behavior (the amount smoked, and how one smokes).

4. Study Procedures

- a. Study design, including the sequence and timing of study procedures (distinguish research procedures from those that are part of routine care).

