Demand Metrics: Reinforcement will be assessed by the 2 essential demand metrics: demand intensity and demand elasticity; which are calculated with nonlinear regression using the exponential demand equation (Hursh & Silberberg, 2008). Auxiliary metrics (Pmax, Omax, breakpoint) will also be examined, although these are derivative of the essential metrics. Demand elasticity and demand intensity will be calculated for each cigarette type (greenwashed or control) as it escalates in price and the alternative cigarette price remains fixed. Cross-price elasticity will be calculated to quantify the effect of increasing greenwashed cigarette work requirements on control cigarette consumption, and vice-versa. These measures will indicate how greenwashing perceptions may increase smoking. Greater demand intensity for greenwashed cigarettes compared to nongreenwashed cigarettes would indicate that greenwashing would increase cigarette consumption even at the lower end of commercial price ranges. Greater demand elasticity for greenwashed cigarettes compared to nongreenwashed cigarettes would indicate that greenwashing would increase cigarette consumption at higher prices in the commercial market, even if greenwashing had little or no effect at lower prices. By examining reinforcer interactions (cross-price elasticity), demand analyses can inform the degree to which smokers would pay more for greenwashed cigarettes even if non-greenwashed cigarettes were available at a lower price.

- b. Secondary outcome variables.

Smoking Topography: We will collect six measures of smoking topography: total puff volume, mean puff volume, mean puff duration, mean inter-puff interval, mean maximum flow rate, and number of puffs. These data will be collected by ad lib smoking using our existing custom smoking topography system currently in use in our laboratory (IRB00107178). Our current research uses this topography system to help participants achieve a target volume per puff, but is already fully functional in its ability to measure topography of ad lib smoking. These measures will indicate the effect of greenwashing on how people smoke cigarettes in more damaging ways, for example, by smoking more deeply (greater puff volume), faster (greater maximum flow rate, lower inter-puff interval), or with increased time in lungs (greater puff duration).

- c. Statistical plan including sample size justification and interim data analysis.

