Analysis of Demand Curves: A paired-samples *t*-test will examine each demand metric, with data transformations of each demand metric if non-normally distributed (square root transform of Q0 and natural-log transform of α). We expect different demand profiles (greater demand intensity, and lower elasticity of demand) when cigarettes are greenwashed compared to control cigarettes.

Analysis of Cross-Price Elasticity: To calculate cross price elasticity of cigarettes, any instances of zero self administrations within a block will be coded as 0.5 because the logarithm

Date: February 18, 2023

Principal Investigator: [name].

Application Number: IRB00264306

NCT04595279

of zero is undefined. Then, a linear regression will be performed on the log10 of consumption means vs. the log10 of unit prices. The resulting slope of this regression line will be the cross-price elasticity.

Analysis of Smoking Topography: Paired-samples *t*-tests will be used to compare measures of smoking topography between the greenwashed and control cigarettes.

Statistical power:

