Using data from an ongoing operant demand study in our lab evaluating the substitutability of reduced-nicotine content cigarettes for full-nicotine cigarettes (grant R01DA042527), elasticity (α) of reduced-nicotine cigarettes was significantly greater than that of full-nicotine cigarettes (Cohen's $d = 1.33$). Although these analyses were limited to single-item demand (i.e. cigarettes not concurrently available), the same underlying principles are applicable to the current analysis. Assuming an effect size half as large ($d=.67$), a sample size of $N = 20$ would provide power $\geq 80\%$ (two-tailed; $\alpha=.05$) to detect a main effect of greenwashing tactics on demand metrics. Our proposed sample size of $N = 35$ would provide between 97-98% power in the current analyses comparing demand metrics between the cigarette packaging types, assuming an effect size of $d=0.67$ or 0.70 , respectively. A previous study comparing smoking topography of water pipe tobacco with and without graphic warning labels demonstrated significantly reduced total puff volume in the water pipe with the graphic warning label relative to the unlabeled pipe ($d=0.49$) (Maziak et al., 2019). Using the effect size from Maziak et al. (2019), which is comparable to the current approach, a sample size of $N = 35$ would provide $\geq 80\%$ power (two-tailed; $\alpha=.05$). Because the published topography data represent the smallest encountered effect size among the outcomes, we are powering the study to address this effect, which will provide a sample size that is beyond sufficiently-powered to address the aforementioned demand outcomes.

Demand metrics (demand intensity, demand elasticity, cross-price elasticity) and topography measures (total puff volume, mean puff volume, mean puff duration, mean inter-puff interval, mean maximum flow rate, and total puff number) will be compared between control and greenwashed cigarettes using paired-samples *t*-tests. Power analyses were performed for all primary behavioral economic and topography variables. Because topography measures showed the smallest anticipated effect based on published data ($d = 0.49$), we have conservatively based our sample size on topography. Despite this conservative estimation, if non-significant trends are observed suggesting potential effects, the proposed research will provide excellent data for informing power for future studies.

- d. Early stopping rules.

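### Section 7a treats greater price elasticity as favouring greenwashing, contrary to the plan's own definition and prediction, and no rule links the tests of the two essential demand metrics

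*Combined protocol and SAP*

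**What the plan says.** **Direction of elasticity.** Section 3 (Background) defines demand elasticity as how strongly consumption responds to a change in price. Section 2 (Objectives) hypothesises that greenwashed cigarettes will "b) show reduced sensitivity to price compared to non-greenwashed cigarettes". Section 7c (Analysis of Demand Curves) expects "greater demand intensity, and lower elasticity of demand) when cigarettes are greenwashed compared to control cigarettes". Section 7a (Primary outcome variables) says: "Greater demand elasticity for greenwashed cigarettes compared to nongreenwashed cigarettes would indicate that greenwashing would increase cigarette consumption at higher prices". Section 3 has a near-identical sentence.

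**Tests and level.** Section 7a states: "Reinforcement will be assessed by the 2 essential demand metrics: demand intensity and demand elasticity". Under the same primary heading it adds: "Cross-price elasticity will be calculated to quantify the effect of increasing greenwashed cigarette work requirements on control cigarette consumption", and the reverse. Section 7c says that a paired t-test "will examine each demand metric, with data transformations of each demand metric if non-normally distributed". The paired t-test for cross-price elasticity appears only in the closing paragraph of the power text, which lists "Demand metrics (demand intensity, demand elasticity, cross-price elasticity) and topography measures" together. Two-sided 0.05 appears only in the power calculations. No section gives a testing order, an adjustment or a rule for combining the demand metrics, and no direction is predicted for the cross-price difference.

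**How the results may be used.** Section 2 gives separate hypotheses, and section 7a gives intensity and elasticity separate meanings (lower versus higher prices). On the other side, section 3 says: "A difference in any behavioral economic demand metric would be meaningful for the cigarette market". The power text speaks of a main effect of greenwashing on the demand metrics as a group, and section 9 expects the study to inform FDA policy.

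**The concern.** The elasticity sentence sits in the section that defines the primary outcomes. If elasticity is sensitivity to price, a significantly greater value for greenwashed cigarettes means that consumption falls faster as their price rises. That is the opposite of what the investigators expect. With two-sided tests, a significant elasticity difference in either direction could then be cited from the protocol as favouring greenwashing: lower elasticity from sections 2 and 7c, greater elasticity from sections 3 and 7a.

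The second matter is smaller. Two essential metrics are each tested at the full 0.05, and the plan does not say whether one significant metric is enough to claim that greenwashing affects demand. If it is, the error rate for that claim is above the level used in the power section. Without a stated rule, the choice between separate claims and one overall claim can be made after the results are known.

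**Working it through.** **1. Elasticity passages side by side.**

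| Place | Direction said to favour greenwashing |
|---|---|
| Section 2, hypothesis (b) | less sensitivity to price |
| Section 7c, Analysis of Demand Curves | lower elasticity |
| Section 3, rationale for demand analysis | greater elasticity |
| Section 7a, primary outcomes | greater elasticity |

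Under the definition in section 3, the first two rows agree with each other and the last two contradict them. The power text in section 7c labels elasticity as α, so the predicted direction is a smaller α.

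**2. The plan's own power figures.** Inputs from section 7c: paired t-test, two-sided 0.05; d = 0.67 (half of 1.33), 0.70 and 0.49; N = 20 and 35. Power comes from the noncentral t distribution with df = N − 1 and noncentrality d√N.

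- N = 20, d = 0.67: noncentrality 3.00, power 81.1% (plan: at least 80%)
- N = 35, d = 0.67: noncentrality 3.96, power 97.1% (plan: 97%)
- N = 35, d = 0.70: noncentrality 4.14, power 98.0% (plan: 98%)
- N = 35, d = 0.49: noncentrality 2.90, power 80.4% (plan: at least 80%)

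All reproduce with the full 0.05 on each test, so no alpha was set aside for multiplicity.

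**3. Chance of at least one false difference, if any one metric can carry the claim.**

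- Two metrics, either direction: upper bound 2 × 0.05 = 10%; if independent, 1 − 0.95² = 9.75%.
- Two metrics, favourable direction only: upper bound 2 × 0.025 = 5%; if independent, 1 − 0.975² = 4.9%. A single test gives 2.5%.
- Three metrics (with cross-price elasticity), if independent: 1 − 0.95³ = 14.3% in either direction; 1 − 0.975³ = 7.3% in the favourable direction, once one is named for each metric.

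The documents give no correlations between metrics. In 200,000 simulated trials of paired t-tests at N = 35, two metrics gave about 9.1% at an assumed correlation of 0.5 and about 7% at 0.9, counting either direction.

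**4. Holm over the two essential metrics.** The smaller p-value is compared with 0.025. If it passes, the other is compared with 0.05. The simulated overall two-sided error is 4.9%, 4.7% and 3.7% at correlations 0, 0.5 and 0.9.

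Worst-case power for a metric (only that effect is real) is taken as its power at 0.025 with N = 35:

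- d = 0.67: 97.1% falls to 94.2%
- d = 0.49: 80.4% falls to 70.9%

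If both effects are real at d = 0.67, simulated Holm power per metric is 96.8%, 96.5% and 95.7% at correlations 0, 0.5 and 0.9.

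**The case against.** A reader might infer that the plan runs a 10% to 14% false-positive rate on its primary claim. The documents do not support that. They state separate hypotheses and interpret the two essential metrics separately, and no pooled claim is written down. The remark in section 3 that a difference in any metric matters explains why demand curves were preferred to a progressive ratio or discrete choice; it is not a decision rule. Section 9 answers a form heading on benefits. The 10% and 14% figures also count false results in both directions, whereas the claim of interest has one direction. Intensity and elasticity come from the same fitted curve in the same people, so they may well be correlated, which lowers the rate. The 14% further depends on counting cross-price elasticity, although section 7a calls only two metrics essential. All of this stands, and it limits the second matter to a conditional one.

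It can also be said that the elasticity sentence is a slip whose intent is plain from the rest of the sentence, and that it leaves the two-sided error rates unchanged. Both are true. But the sentence is part of the primary outcome section, and it reverses the reading of a significant result. It therefore needs correcting whatever is decided about multiplicity.

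A reader might also extend the family to the six topography measures because they share the closing sentence of the power text. Section 7b makes them secondary, so the documents do not support that either.

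**Conclusion.** The elasticity wording in sections 3 and 7a is wrong as written. It conflicts with the definition in section 3 and with the predictions in sections 2 and 7c, and this rests on the text alone.

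The missing rule across the two essential metrics is a real but modest gap. Separate claims keep 5% each and need no adjustment. Only if either metric may carry a claim about demand does the false-difference rate rise: at most 10% in either direction (9.75% if independent, about 7% at an assumed correlation of 0.9), and at most 5% in the favourable direction against 2.5% for one test. The 14.3% and 7.3% figures apply only if cross-price elasticity is counted as a third primary metric and the metrics are independent.

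The power figures assume that all 35 participants contribute a paired value. They also assume that d = 0.67, which the plan derives from elasticity alone, applies to intensity.

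**What to change.** **Elasticity wording.** In the sentences in sections 3 and 7a, replace greater demand elasticity with lower demand elasticity (smaller α), to match sections 2 and 7c. This costs nothing.

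**Rule across metrics.** Add to section 7c: *Demand intensity and demand elasticity are tested with Holm's procedure at an overall two-sided 0.05 (smaller p-value against 0.025, then the other against 0.05). An effect of greenwashing on demand is claimed only from a metric that is significant under this procedure. Cross-price elasticity, the auxiliary metrics and the topography measures are supportive for that claim.*

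N stays at 35. At the plan's demand effect of d = 0.67, worst-case power per metric falls by 2.9 percentage points, to 94.2%. At d = 0.49 the loss would be 9.5 points, to 70.9%, but the plan takes that effect from a waterpipe topography study and does not assume it for demand.
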